The TACTiC study will be conducted in 30-50 markets throughout the United States. All visits will be completed utilizing virtual methods such as virtual visits conducted by the Central Medical Operations Group (CMOG) study staff. The CMOG is comprised of clinicians that include registered nurses, nurse practitioners, physician assistants and medical doctors. There will be a Virtual Visit 1, 60-day and 120-day phone calls, a Virtual Visit 2 and a 30-day follow-up phone call post-study drug discontinuation to assess participants status with regard to adverse events (AEs).

Inclusion Criteria

- 1 Males, 20-75 years of age
- 2 Females, 20-75 years of age (This inclusion criterion will be applied until 50 females under the age of 50 years complete the initial TASS assessment in the Web App. After this quota of 50 females under the age of 50 years old is met, the inclusion criterion will be revised to females 50-75 years old).
- 3 Respond to advertising regarding a concern about high cholesterol or heart health
- 4 Able to read speak and understand English

Additional Criteria for Inclusion for Actual Use (at Virtual Visit 1)

- 1 Participant reads and signs the Informed Consent form.

Exclusion Criteria

- 1 The participant or anyone in their household is currently employed by any of the following:
 - A pharmacy or pharmaceutical company
 - A consumer healthcare company
 - A manufacturer of medicines
 - A managed care or health insurance company
 - A healthcare practice
 - An employee of AstraZeneca or Concentrics Research
- 2 The participant has ever been trained or employed as a healthcare professional (physician, nurse, nurse practitioner, physician assistant, pharmacist).
- 3 The participant has, or cannot recall whether he/she has, received an investigational therapy as part of a clinical trial in the previous twelve (12) months.
- 4 The participant is not willing to provide contact information.
- 5 Previous enrollment in the present study.

- 6 The participant has a mailing address in Alaska, or their mailing address is a Post Office (PO) Box.
- 7 The participant is not willing to complete an eDiary.

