4.2 Scientific Rationale for Study Design

Heart disease is the leading cause of death for both men and women in the United States and worldwide (Mercado et al 2015). Elevated cholesterol is a key risk factor for heart disease, and while lowering cholesterol with statin drugs reduces cardiovascular morbidity and mortality, only about half of the people in the United States who require therapy are currently being treated (Mercado et al 2015). This represents a substantial public health issue for the United States. There are numerous reasons why people are not treated, but what is clear is that easier access to safe, effective, and affordable therapy would have a significant positive impact on public health. One way to simplify access to statin therapy would be to make it available to consumers without a prescription (e.g., OTC). Past attempts to achieve an OTC switch for statin treatment have failed due to concerns about the efficacy of the statins that were tested, and because consumers were unable to properly self-select. The Crestor OTC program addresses these two concerns by using Crestor 5 mg (a safe and highly effective dose of rosuvastatin with minimal interactions) and a TASS tool that ensures the medicine is only made available to consumers for whom it is appropriate (AstraZeneca Pharmaceuticals LP 2021). Completed studies evaluating DFL comprehension, CIL comprehension, Web App comprehension, Human Factors, Targeted Self-Selection and All-comers Self-Selection have shown that this approach is viable. Based on the success of these non-interventional behavioral studies, AstraZeneca is ready to proceed with the AUS.

The AUS is designed to test the ability of participants to input their medical data into a Web App in order to get a correct TASS outcome for the initial purchase as well as to assess their ability to correctly enter their ongoing health status into the Web App to demonstrate proper use of nonprescription rosuvastatin during the use period. Nonprescription rosuvastatin will only be available online for purchase via the Web App and direct shipment to the participant. It is intended for use by:

- Males 20-39 years of age with high LDL-C (160-189 mg/dL) plus family history of cardiovascular disease (CVD) (mother/sister younger than 65 years of age or father/brother younger than 55 years of age)
- Females 50-75 years of age with ASCVD risk score between 7.5% - <20% and LDL-C 70-189 mg/dL

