5.2 Inclusion Criteria

Participants are eligible to be included in the study only if all of the following criteria apply:

- 1 Males, 20-75 years of age.
- 2 Females, 20-75 years of age (This inclusion criterion will be applied until 50 females under the age of 50 years complete the initial TASS assessment in the Web App. After this quota of 50 women under the age of 50 years old is met, the inclusion criterion will be revised to women 50-75 years old).

- 3 Respond to advertising regarding a concern about high cholesterol or heart health.
- 4 Able to read speak and understand English.

Additional Criteria for Inclusion into Actual Use (at Virtual Visit 1)

- 1 Participant reads and signs the Informed Consent form.

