2 ANALYSIS SETS

2.1 Definition of Analysis Sets

The analysis populations to be used in the study are defined as follows:

Pre-Screen Eligible and Registered Population – The Pre-Screen eligible and registered population includes all subjects who are eligible after completing the pre-screener either online or by calling the Call Center and registered for pre-screener follow-up.

Pre-Screen Failure Population – The Pre-Screen Failure population is comprised of all subjects who meet one of the following categories:

- Did not meet SS inclusion criteria or met SS exclusion criteria

- Qualified refused - Patients with OK to Use outcome but did not move forward with study
- Received Web App link but did not complete the TASS assessment
- Received Web App link and received a “Do Not Use” outcome
- Received Web App link and received an “Ask a Doctor” outcome and did not go back into the Web App and indicate a doctor said it was okay to proceed
- Received Web App link, received an “OK to Use” outcome or an “Ask a Doctor” outcome and indicated a doctor said it was okay to proceed but never created a Web App account
- Received Web App link, received an “OK to Use” outcome or an “Ask a Doctor” outcome and indicated a doctor said it was okay to proceed, created a Web App account but did not make an initial purchase of study drug
- Received Web App link, received an “OK to Use” outcome or an “Ask a Doctor” outcome and indicated a doctor said it was okay to proceed, created a Web App account, made an initial purchase of study drug but did not schedule their first visit
- Received Web App link, received an “OK to Use” outcome or an “Ask a Doctor” outcome and indicated a doctor said it was okay to proceed, scheduled their first visit but did not sign the Informed Consent Form (ICF) (either did not show for their first visit or showed but decided not to sign ICF)

SS Population – The SS population includes all participants who sign the ICF.

AUS Screen Failure Population – The AUS Screen Failure population includes all participants in the SS population who meet the AUS exclusion criteria.

AUS Intent to Treat (ITT) Population – The AUS ITT population consists of all participants in the SS population who meet all eligibility for AUS and have investigational product (IP) delivered to their address.

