3 PRIMARY AND SECONDARY VARIABLES

3.1 Participant Disposition

Potential subjects who are screened for the purpose of determining eligibility for the study but do not sign consent in the study are defined as “pre-screen failures.” Pre-screen failures are defined as all subjects who meet one of the following categories:

- Did not meet SS inclusion criteria or met SS exclusion criteria
- Qualified refused
- Received Web App link but did not complete the TASS assessment
- Received Web App link and received a “Do Not Use” outcome
- Received Web App link and received an “Ask a Doctor” outcome and did not go back into the Web App and indicate a doctor said it was okay to proceed
- Received Web App link, received an “OK to Use” outcome or an “Ask a Doctor” outcome and indicated a doctor said it was okay to proceed but never created a Web App account
- Received Web App link, received an “OK to Use” outcome or an “Ask a Doctor” outcome and indicated a doctor said it was okay to proceed, created a Web App account but did not make an initial purchase of study drug
- Received Web App link, received an “OK to Use” outcome or an “Ask a Doctor” outcome and indicated a doctor said it was okay to proceed, created a Web App account, made an initial purchase of study drug but did not schedule their first visit
- Received Web App link, received an “OK to Use” outcome or an “Ask a Doctor” outcome and indicated a doctor said it was okay to proceed, scheduled their first visit but did not sign the ICF (either did not show for their first visit or showed but decided not to sign ICF)

Individuals who do not meet the criteria for participation in this study (i.e., pre-screen failures) may not be rescreened.

“Enrolled” is defined as a participant’s agreement to participate in the clinical study following completion of the ICF.

Once the initial targeted medical and medication history has been gathered by the CMOG, participants may not be eligible to continue into the actual use period of the study if they are determined to be pregnant, breastfeeding, or have a severe allergy to rosuvastatin. These participants are classified as “AUS Screen Failures.”

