4.2 Analysis methods

4.2.1 Analysis of Baseline Participant Characteristics and Diagnostics

For subjects who are Pre-Screen Failures:

- The categorical baseline characteristics of age group, sex at birth, education level, race, employment status, and annual household income will be summarized using frequency counts and percentages based on the data captured in the Pre-Screener. The denominator for the percentages will be the total number of subjects in the Pre-Screen Failure population overall.

Subjects can choose to complete part of the pre-screening for SS eligibility criteria via an online pre-screener or call the Call Center to complete all pre-screening questions. Anyone that qualifies after completing the online pre-screener is directed to call the Call Center to complete additional pre-screening questions. Those that do not qualify are not directed to call the Call Center to complete the additional pre-screening questions.

- Subjects who choose to complete the online pre-screener and do not qualify or subjects who qualify via the online pre-screener but do not call the Call Center to answer the follow-up pre-screening questions will have incomplete prescreening data.

The baseline subject characteristics and demographics will be summarized for the Pre-Screen Failure population overall and by each pre-screen failure category as defined in [Section 2.1](#).

The Pre-Screen Failure population will be used to analyze the initial subject TASS outcome and reason for outcome in women under the age of 50 years old. The subject TASS entries entered by women under the age of 50 years old will be listed.

Recruitment by geographic region, based on the U.S. Census Bureau, and state for the individuals who were sent a TASS link for the pre-screen eligible and registered population will be presented. The corresponding information for the SS population is also presented.

For all participants in the SS population:

- The categorical baseline characteristics of education level, employment status, and household income will be summarized using frequency counts and percentages based on the

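### The table of initial TASS outcomes in women under 50 leaves out any such woman who passes and consents, so it can only err in the Web App's favour

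*SAP*

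**What the plan says.** **The analysis.** SAP 4.2.1, under the heading for pre-screen failures, states: "The Pre-Screen Failure population will be used to analyze the initial subject TASS outcome and reason for outcome in women under the age of" 50. No other population is named. The next sentence promises a listing of these women's TASS entries without naming a population.

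**Who is in that population.** SAP 3.1 fixes the boundary at consent when it introduces the term pre-screen failure: "Potential subjects who are screened for the purpose of determining eligibility for the study but do not sign consent in the study are defined as" such. The last category in SAP 2.1 covers people who passed the TASS and "scheduled their first visit but did not sign the Informed Consent Form (ICF"). Everyone else who reaches that step goes elsewhere: "The SS population includes all participants who sign the ICF". The two sets do not overlap.

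**Whom the protocol recruits.** Protocol 5.2 admits women from age 20 and adds: "This inclusion criterion will be applied until 50 females under the age of 50 years complete the initial TASS assessment in the Web App". The count is taken at TASS completion, not at failure and not at consent. The rationale for Amendment 7 in Protocol Appendix F says the same: TASS completion comes before enrollment, so enrollment is not needed to fill the quota.

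**Who is meant to use the product.** The entries for women in Protocol 4.2 start at age 50, for example "Females 50-75 years of age with ASCVD risk score between 7.5% - <20% and LDL-C 70-189 mg/dL".

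**The concern.** A quota of women outside the intended age range, followed by a table of their outcomes and reasons, looks like a check that the tool turns them away. For that check, the result of interest is a woman under 50 who is allowed through. Only someone allowed through can buy, attend Virtual Visit 1 and sign the ICF. Restricting the table to people who did not sign therefore conditions it on something that follows from the outcome being tabulated. The restriction can remove wrong passes. It can never remove a correct Do Not Use result.

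What is at stake is how a favourable table can be read. If it shows few or no women under 50 getting through, the reader cannot tell whether the tool stopped them or whether those it missed went on to consent and were moved to the SS population.

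**Working it through.** **Step 1. Trace each route through the plan's definitions (SAP 2.1 and 3.1).**

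| Woman under 50 who completes the initial TASS | Population | In the SAP 4.2.1 table? |
|---|---|---|
| Do Not Use | Pre-Screen Failure | Yes |
| Ask a Doctor, no permission recorded | Pre-Screen Failure | Yes |
| Passes; no account, no purchase or no visit scheduled | Pre-Screen Failure | Yes, as a visible wrong pass |
| Passes, schedules, does not sign | Pre-Screen Failure | Yes, as a visible wrong pass |
| Passes and signs the ICF | SS | No |

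Only the last row is lost, and it contains only passes. The bias therefore has one direction.

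**Step 2. How many passes go on to sign?** The plan gives no rate for women under 50. Its overall funnel (SAP Table 1) has 1,800 OK to Use, 1,525 scheduled (85%) and 1,220 consented (80%). Check: 1,800 × 0.85 = 1,530, against 1,525 stated; 1,525 × 0.80 = 1,220, as stated. The share of passes who sign is 1,220/1,800 = 67.8%, or 0.85 × 0.80 = 68%. Applying it to women under 50 is an assumption.

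**Step 3. Compare the two denominators.** Let n = 50 (the quota), k = number of wrong passes (assumed) and f = share of these who consent.

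- All TASS completers: k/n, with an exact (Clopper-Pearson) 95% CI.
- Planned table: k(1 − f) / (n − kf).
- When f = 1 the planned table shows 0 of n − k, with upper 95% bound 1 − 0.025^(1/(n − k)).

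For k = 5 and f = 0.678: kf = 3.39; visible passes 5 − 3.39 = 1.61; denominator 50 − 3.39 = 46.61; 1.61/46.61 = 3.5%.

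| k (assumed) | All 50 completers | Planned table, f = 67.8% (expected) | Planned table, f = 100% (extreme) |
|---|---|---|---|
| 0 | 0/50 = 0% (upper bound 7.1%) | same | same |
| 3 | 3/50 = 6.0% (1.3-16.5%) | 0.97/47.97 = 2.0% | 0/47 (upper bound 7.5%) |
| 5 | 5/50 = 10.0% (3.3-21.8%) | 1.61/46.61 = 3.5% | 0/45 (upper bound 7.9%) |
| 10 | 10/50 = 20.0% (10.0-33.7%) | 3.22/43.22 = 7.5% | 0/40 (upper bound 8.8%) |

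At the funnel's consent share, the planned table shows roughly a third of the true rate.

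**Step 4. Does another planned output give the rate?** SAP 4.1.2 names sex and age group as separate subgroups, and the under-50 group includes men. The first co-primary analysis includes these women if they consent, but 5 of 1,220 is 0.4%. SAP Appendix C also recodes an age entry wrong by up to 12 months as correct. No output gives a pass rate for women under 50.

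**The case against.** Four points can be made for the plan.

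1. **Not every wrong pass is hidden.** A reader might infer that the table must show complete success whatever the tool does. The documents do not support that: a woman who passes but never creates an account, buys, schedules or signs remains a pre-screen failure and is visible in the table. The zero counts in the last column above are the extreme case, not the expectation. This stands in full.

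2. **Consenting women are not lost to the study.** A reader might also infer that nothing else would reveal them. In fact they are in the first co-primary denominator, where a clinician outcome of Do Not Use makes them incorrect unless mitigated. Reasons for clinician outcomes (SAP 4.2.2) and incorrect entries by TASS question (SAP 4.2.4) are tabulated by subgroup. Recruitment stops at 75, so an age-based Do Not Use among women would be expected to mean under 50. Entries and baseline data are listed by participant. This stands as to identifying individuals, but it yields no rate for the group.

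3. **The purpose is inferred.** The table sits among baseline characteristics, with no threshold, hypothesis or interval, and neither document calls it a check on the tool. This stands. The inference rests on the dedicated quota, the intended age range and the choice of outcome and reason as the items to report.

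4. **No effect on exposure.** It is tempting to present this as a pregnancy-safety gap. The denominator of a descriptive table changes nobody's exposure, and the protocol has separate safeguards: contraception criteria, a pregnancy test at Virtual Visit 1, and exclusion from actual use for pregnancy or breastfeeding. This also stands.

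**Conclusion.** The point holds as a narrow defect in one descriptive table. Its population is defined by not consenting, while the quota it describes is defined by completing the TASS. The women in between are all passes, so the table can only err in the tool's favour.

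The size depends on two quantities that the documents do not give for this group: the number of wrong passes and the share of them who consent. For 5 assumed wrong passes among 50, the table would show about 3.5% in place of 10.0% at the funnel's consent share, and 0 of 45 at the extreme. If no woman under 50 passes, or none who passes consents, the two versions agree.

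Reading OK to Use as an error in this group rests on the intended age range in Protocol 4.2. No co-primary or secondary conclusion depends on the table, so this is a minor correction.

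**What to change.** Replace the sentence in SAP 4.2.1 with one that runs the table on every woman under 50, by pre-screener age, who completed an initial TASS, regardless of outcome or consent and including those in the SS population. Report the number and percentage with OK to Use, Ask a Doctor and Do Not Use, each with an exact 95% CI, and keep the reasons for outcome. State that the accompanying listing covers the same women.

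The cost is one sentence of text and the matching table shell. Age is collected at pre-screening and each TASS outcome is recorded by the Web App, so no new data are needed. The downside is that the figure may look slightly less favourable.

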5.3 Exclusion Criteria

Participants are excluded from the study if any of the following criteria apply:

Exclusion Criteria

- 1 The participant or anyone in their household is currently employed by any of the following:
 - A pharmacy or pharmaceutical company
 - A consumer healthcare company
 - A manufacturer of medicines
 - A managed care or health insurance company
 - A healthcare practice
 - An employee of AstraZeneca or Concentrics Research
- 2 The participant has ever been trained or employed as a healthcare professional (physician, nurse, nurse practitioner, physician assistant, pharmacist).
- 3 The participant has, or cannot recall whether he/she has, received an investigational therapy as part of a clinical trial in the previous twelve (12) months.
- 4 The participant is not willing to provide contact information.
- 5 Previous enrollment in the present study.
- 6 The participant has a mailing address in Alaska, or their mailing address is a Post Office (PO) Box.
- 7 The participant is not willing to complete an eDiary.
- 8 The participant is a woman of childbearing potential and is not following contraception guidelines or is not willing to follow contraception guidelines including practicing abstinence or using at least 1 of the following acceptable methods of birth control for at least 1 month prior to entry into the study and for 1 month after study completion: hormonal – oral, implantable, injectable, or transdermal; mechanical – spermicide in conjunction with a barrier such as a condom or diaphragm; intrauterine device; or surgical sterilization of partner.
- 9 The participant does not have access to the internet.

- 10 The participant does not have an email address or the ability to receive emails.
- 11 The participant responds to the Single Item Literacy Screener 2 (SILS2) question (Chew et al 2008) “How confident are you filling out medical forms by yourself?” with either ‘extremely’ or ‘quite a bit.’ (If the quota for normal literacy is met, but the limited literacy target is not met, the SILS2 exclusion will be used to help increase the percentage of limited literacy participants at Virtual Visit 1. Participants identified as normal literacy by Rapid Estimate of Adult Literacy in Medicine (REALM) testing at Virtual Visit 1 will not be excluded from entry into the treatment phase of the study.)

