3.2.2 Rapid Estimate of Adult Literacy in Medicine (REALM)¹

A REALM test will be administered to determine literacy for those participants who sign the ICF and attend their Virtual Visit 1. The word list will be displayed on the participant’s screen and the interviewer will be able to visually see and hear the participant say each word on the video. Limited Literacy, or a 7th/8th grade reading level and below, is a REALM score less than or equal to 60. Normal literacy, or a high school reading level and above, is a REALM score greater than 60.

A sub-study of the TACTiC Trial will be performed to assess treatment-seeking behaviors in high-risk participants who failed to qualify for TACTiC. Since participants enrolled in the sub-study would pre-screen fail prior to Virtual Visit 1, a REALM test will not be available. To assess the literacy status of subjects evaluated in the sub-study, all participants who have a REALM test in TACTiC will be asked the Single Item Literacy Screener 2 (SILS2) question. The association between the SILS2 and REALM will be used to determine the SILS2 score that best corresponds to limited literacy in a primary prevention CV population.

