 - The SILS2 and REALM data collected in this study will be evaluated in the SS Population to determine the optimal SILS2 threshold for the classification of participants as limited literacy or normal literacy in the sub-study. The screening question, “How confident are you filling out forms by yourself?” (SILS2) will be scored by assigning the values 0, 1, 2, 3, and 4 to the five possible responses to the question, where 0 represents extreme confidence and 4 represents no confidence in independently filling out medical forms. These numerical responses will be compared to the REALM classifications of limited literacy and normal literacy to produce a Receiver Operator Characteristic (ROC) curve. The area under the ROC curve (AUC) will also be provided. Values of sensitivity and specificity will be computed for each SILS2 threshold ($\leq 0, \leq 1, \leq 2, \leq 3, \leq 4$).

The analysis completed for the SS population will be repeated for those participants in the AUS ITT and PP populations.

Disease background and characteristics based on the targeted medical and medication history form will be presented for the SS population overall and by subgroups as well as the AUS ITT and PP populations.

The participant's order preference of the investigational product in increments of 45-day supply, 90-day supply, or mix (started 45d then switched to 90d, or vice versa) will be tabulated by number and percentage.

Additionally, the number and percentage of participants with a verified source for their diagnostic data at Virtual Visit 1 will be summarized overall and by subgroups for each diagnostic variable and source (e.g., doctor/prescription, home test kit, etc.) for those participants in the SS, AUS ITT, and PP populations.

A detailed listing of baseline characteristics and diagnostic data for each participant will also be provided as shown.

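### If the SILS2 recruitment filter is switched on, SILS2-versus-REALM accuracy computed on the whole SS population is biased, because later entrants are selected on the test being evaluated

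*SAP*

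**What the plan says.** Protocol 5.3, exclusion 11, is a conditional recruitment rule: "If the quota for normal literacy is met, but the limited literacy target is not met, the SILS2 exclusion will be used". When active, it removes anyone giving either of the two most confident answers to the SILS2 question. SAP 4.2.1 scores these 0 and 1, on a scale where 4 means no confidence. Selection is on SILS2 and not on the reference test: "Participants identified as normal literacy by Rapid Estimate of Adult Literacy in Medicine (REALM) testing at Virtual Visit 1 will not be excluded".

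The Schedule of Activities places SILS2 in pre-screening. SAP 2.1 opens its list of pre-screen failures with "Did not meet SS inclusion criteria or met SS exclusion criteria", so a person caught by the filter does not reach Virtual Visit 1, where consent and the REALM test take place. By contrast, "The SS population includes all participants who sign the ICF".

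SAP 4.2.1 states that "The SILS2 and REALM data collected in this study will be evaluated in the SS Population to determine the optimal SILS2 threshold" for the sub-study. It asks for an ROC curve, an AUC, and sensitivity and specificity at thresholds from ≤0 to ≤4, and has the SS analyses repeated in the AUS ITT and PP populations. SAP 3.2.2 defines limited literacy as a REALM score of 60 or less. It explains that sub-study subjects will have no REALM, so the SILS2–REALM association "will be used to determine the SILS2 score that best corresponds to limited literacy in a primary prevention CV population".

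Protocol 9.4.4 carries a heading on the SILS2 literacy threshold, but its content is redacted.

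**The concern.** Once the filter is on, only scores 2 to 4 can enter the SS population. Two groups are then missing from that stretch of enrolment: people of limited literacy who report high confidence (missed by the test) and people of normal literacy who report high confidence (correctly classified). The pooled SS set mixes this truncated segment with the unfiltered participants who came before. Sensitivity and specificity are conditional on REALM status, so they are not protected when entry depends on the SILS2 answer.

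The filter also splits the scale at 0–1 versus 2–4, one of the cuts the analysis is meant to judge. At stake is the threshold used to classify literacy in the sub-study, where no REALM exists to show up an error.

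**Working it through.** The documents give no sensitivity, specificity, AUC or SILS2 distribution, so there is no figure to reproduce. They give two items of context. Protocol Table 3 implies an SS population of 1,525 × 0.80 = 1,220. The literacy goal is 100 of at least 500 evaluable, which is 20%.

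**Direction.** Call a score of t or more limited literacy. Let w < 1 be the retention of scores 0–1 relative to scores 2–4 in the pooled set. Let FL and FN be the true shares scoring 0–1 among limited- and normal-literacy people. For t ≥ 2:

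- Se′ = Se / [1 − (1 − w)·FL]
- 1 − Sp′ = (1 − Sp) / [1 − (1 − w)·FN]

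Both denominators are below 1, so Se′ > Se and Sp′ < Sp. The cut t = 1 moves the same way. The SAP's ≤4 threshold puts everyone on one side and cannot be biased.

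**Worked case (assumed values).** Prevalence of limited literacy is 10%. Scores 0 to 4 are distributed 0.30, 0.25, 0.25, 0.12, 0.08 in limited literacy and 0.60, 0.25, 0.10, 0.03, 0.02 in normal literacy. Without the filter, a cut of 2 or more has Se = 0.45 and Sp = 0.85. The share scoring 2 or more is 0.10 × 0.45 + 0.90 × 0.15 = 0.18. Let a fraction f = 0.25 of the SS population enrol under the filter.

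- Limited, score ≥2: 0.75 × 0.045 + 0.25 × 0.045/0.18 = 0.09625. Limited, score 0–1: 0.75 × 0.055 = 0.04125. Se′ = 0.09625/0.1375 = 0.70.
- Normal, score ≥2: 0.75 × 0.135 + 0.25 × 0.135/0.18 = 0.28875. Normal, score 0–1: 0.75 × 0.765 = 0.57375. Sp′ = 0.57375/0.8625 = 0.67.

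The same calculation over three assumed distributions (moderate as above; strong, Se/Sp 0.70/0.90; weak, 0.30/0.80) and prevalences of 10% and 20%, at the cut of 2 or more:

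| f | Sensitivity, moderate, 10% | Specificity, moderate, 10% | Sensitivity shift, all cases | Specificity shift, all cases |
|---|---|---|---|---|
| 0 | 0.45 | 0.85 | none | none |
| 10% | 0.57 | 0.78 | up 8 to 12 points | down 4 to 8 points |
| 25% | 0.70 | 0.67 | up 15 to 25 points | down 12 to 19 points |
| 50% | 0.84 | 0.46 | up 23 to 41 points | down 28 to 39 points |

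**AUC** moves less, and in either direction. In the moderate 10% case it is 0.691 unfiltered, 0.712 at f = 25% and 0.684 at f = 50%.

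**Choice of cut.** The readable SAP names no criterion for the optimal threshold, so Youden's index (Se + Sp − 1) is assumed here. In the moderate case the cuts ≥1 and ≥2 tie at 0.30 without the filter. At f = 25% and 10% prevalence they become 0.306 and 0.365, favouring ≥2, the filter's own split. The weak case also ties at first and then favours ≥2. In the strong case ≥2 is best without the filter and stays best for f up to 50%.

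**The case against.** Several points on the other side stand.

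- **The filter may never be used.** Activation is optional. The documents give no numeric normal-literacy quota and no activation date.
- **Direction depends on a convention.** The SAP lists thresholds as ≤t without naming the positive class. If a low score is read as a positive test for normal literacy, the labels swap: sensitivity falls and specificity rises. The distortion is the same.
- **Some quantities are safe.** Selection on SILS2 leaves the probability of limited literacy at a given score undistorted. The SAP, however, asks for sensitivity, specificity and AUC.
- **A prevalence of 20% is an awkward illustration.** It equals the 100-of-500 goal, where the filter would not be expected to trigger. The worked case therefore uses 10%; the shifts at 20% are somewhat smaller.
- **SILS2 may be asked again.** SAP 3.2.2 says that everyone with a REALM test will be asked the question. If a second answer at Virtual Visit 1 were the one analysed, some scores of 0–1 could reappear and the bias would be smaller.
- **Protocol 9.4.4 is redacted.** It is only possible to say that the readable SAP 4.2.1 contains no safeguard.

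Two stronger readings are tempting. A reader might infer that the sub-study's limited-literacy percentage will be wrong by the amounts in the table. The documents do not support that: the analysis selects a threshold, and no readable text applies its sensitivity or specificity to correct the percentage, so that percentage is harmed only if the chosen cut changes. In the illustrations the preference shifts only by breaking a tie. A reader might also infer that the trial's literacy results are compromised. They are not, because the literacy subgroups in SAP 4.1.2 are defined by REALM.

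**Conclusion.** The point holds conditionally. If exclusion 11 is activated, the SILS2 accuracy figures on the pooled SS population are biased at every informative cut, and the AUS ITT and PP repeats inherit the problem as subsets. With higher scores taken as limited literacy, sensitivity is too high and specificity too low, whatever distribution is assumed. AUC can move either way, and the choice between neighbouring cuts may tilt towards the filter's own.

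The size cannot be settled from the documents. The shifts above rest on assumed SILS2 distributions, prevalences and filtered shares, and on the analysed SILS2 answer being the one used for screening. With f = 0 this bias vanishes. The consequence is confined to the sub-study's literacy classification and does not touch the co-primary endpoints or the REALM subgroups.

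**What to change.** In SAP 4.2.1, record whether and when the SILS2 exclusion was activated, and choose the threshold by one of two routes:

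1. Use only SS participants pre-screened before activation.
2. Use the pooled SS sample, weighting each SILS2 score by its share among pre-activation SS participants divided by its share in the pooled sample. All pre-screened callers are the wrong reference, because they differ from the roughly 1,220 who consent.

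In the worked case route 2 recovers the true values. Scores 0–1 get weight 0.82/0.615 = 1.333 and scores 2–4 get 0.18/0.385 = 0.4675. Then Se = 0.09625 × 0.4675 / (0.09625 × 0.4675 + 0.04125 × 1.333) = 0.045/0.100 = 0.45. This assumes that the relation between SILS2 and REALM does not drift over recruitment.

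Report the unweighted full-SS result as descriptive only. If the filter is never used, nothing changes.

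The cost is precision. In the worked case route 1 keeps 0.75 × 1,220 = 915 participants and about 0.10 × 915 ≈ 92 of limited literacy, against 0.1375 × 1,220 ≈ 168 in the pooled set. The standard error of a sensitivity of 0.45 is then √(0.45 × 0.55/92) ≈ 5 points, against a bias of 25 points. If the filter runs for long, the loss is larger.
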